7.2 Participant Discontinuation/Withdrawal from the Study

[Participants are free to withdraw from participation in the study at any time upon request. The PI may discontinue or withdraw a participant from the study for the following reasons:

• Participants may be withdrawn from the study by staff if deemed necessary for their health or safety.

We anticipate that some participants may withdraw. We do not expect early termination of participation due to patient or investigator withdrawal to have any impact on safety or well-being of participants. Patients who withdraw for AE will be evaluated by trained staff for safety.

Participants who enroll in the study (i.e., sign consent and pass screening) and are subsequently withdrawn will be replaced.]

7.3 Lost To Follow-Up

[A participant will be considered lost to follow-up if they fail to return for a scheduled visit and/or are unable to be contacted by the study site staff. If a patient fails to appear for a scheduled visit, staff will attempt to contact and reschedule if the patient wishes and is able to continue in the study. Staff will reach out at least 3 times, and if patient continues to be unreachable, they will be considered lost to follow-up.]

[MagPro X100 Stimulator, Cool-B65 Butterfly Coil]

Page 24 of 39

8 STUDY ASSESSMENT AND PROCEDURES

8.1 Efficacy Assessments

[Participants complete the following for screening: Structured interview for Diagnostic and Statistical Manual of Mental Disorders 5th Edition (DSM-V), the Montgomery-Asberg Depression Rating Scale (MADRS), the Young Mania Rating Scale (YMRS), the Oldfield Assessment for Handedness (handedness will be included in data analysis but is not an exclusionary criterion), and screening for dementia (MMSE >24).

Once enrolled, patients will also complete an MRI scan. MRI data will be acquired on a 3 Tesla Siemens Prisma scanner using a 64 channel head coil (Erlangen, Germany). Our acquisitions are optimized for Siemens Prisma scanners and are rigorously tested as part of the human connectome project (HCP). In the rs-fMRI targeting session T1-weighted, T2-weighted, , and rs-fMRI (2x 8 min) scans will be collected using the 64-channel head coil. We will use the structural and diffusion data to create finite-element models of the electric field for varying coil orientations at the individualized site of stimulation and use these models to optimize the coil orientation for each subject [12].

Patients will complete the TMS administration for 5 consecutive days. They will also complete the MADRS on each day. Following completion of treatment, participants will complete another MRI scan and another MADRS. Patients will also complete a Scale for Suicide Ideation (SSI) and neurocognitive assessments pre and post-treatment.

The data collected to be included in efficacy analyses (pre- and post-treatment) will be the measures of depression severity (MADRS), Antidepressant Treatment History Form (ATHF) data, psychotropic medication at baseline, an optional "The Battleship Task" computational task (which examines how well participants are able to learn a set of shapes that are hidden in a grid), and resting state functional connectivity data (using DLPFC as a seed regions). The primary outcomes will be response to TMS as evidenced by change in MADRS scores for depression severity from the pre-treatment baseline to the end of the 5-day treatment course. The secondary outcome will be change in functional connectivity from pre-treatment to post-treatment using MRI of the brain.]

8.2 Safety and Other Assessments

[Participants will complete the following in order to determine their eligibility for the project: Structured interview for Diagnostic and Statistical Manual of Mental Disorders 5th Edition (DSM-V), the Montgomery-Asberg Depression Rating Scale (MADRS), the Young Mania Rating Scale (YMRS), the Oldfield Assessment for Handedness (handedness will be included in data analysis but is not an exclusionary criterion), and screening for dementia (MMSE >24).

In addition, patients will complete safety screening for both the MRI scan and the TMS administration, screening out individuals who may not be able to complete these tasks.

[MagPro X100 Stimulator, Cool-B65 Butterfly Coil]

Page 25 of 39

Throughout treatment, patients will be monitored by certified personnel. MADRS will be completed during each day of TMS treatment, which will allow staff to monitor symptom severity for safety as well. Any safety concerns will be brought to the PI and necessary personnel.]

8.3 Adverse Events and Serious Adverse Events

8.3.1 Definition of Adverse Events (AE)

[An adverse event (AE) is any untoward medical occurrence associated with the use of an intervention in humans, whether or not considered intervention related. Intercurrent illnesses or injuries should be regarded as adverse events. A pre-existing condition should be recorded as an adverse event if the frequency, intensity or the character of the condition changes.]

8.3.2 Definition of Serious Adverse Events (SAE)

[Serious Adverse Events (SAE)

Adverse events are classified as serious or non-serious. A serious adverse event is any AE that, in the view of the sponsor-investigator, is:

- fatal
- life-threatening
- requires or prolongs hospital stay
- results in persistent or significant disability or incapacity
- a congenital anomaly or birth defect
- an important medical event when the event does not fit the other outcomes, but the event may jeopardize the patient and may require medical or surgical intervention (treatment) to prevent one of the other outcomes.
- required intervention to prevent permanent impairment or damage (for devices only)

Important medical events are those that may not be immediately life threatening but are clearly of major clinical significance. They may jeopardize the subject and may require intervention to prevent one of the other serious outcomes noted above. For example, drug overdose or abuse, a seizure that did not result in in-patient hospitalization, or intensive treatment of bronchospasm in an emergency department would typically be considered serious.]

8.3.3 Unanticipated Adverse Device Effect (UADE)

[Unanticipated Adverse Device Effect (UADE)

A UADE is any serious adverse effect on health or safety, or any life-threatening problem or death caused by, or associated with, a device, if that effect, problem, or death was not previously

[MagPro X100 Stimulator, Cool-B65 Butterfly Coil]

Page 26 of 39

identified in nature, severity, or degree of incidence in the investigational plan or application, or any other unanticipated serious problem associated with a device that relates to the rights, safety, or welfare of subjects.]

8.3.4 Classification of an Adverse Event

8.3.4.1 Severity of Event

[For adverse events (AEs) not included in the protocol defined grading system, the following guidelines will be used to describe severity.

- Mild Events require minimal or no treatment and do not interfere with the participant's daily activities.
- Moderate Events result in a low level of inconvenience or concern with the therapeutic measures. Moderate events may cause some interference with functioning.
- Severe Events interrupt a participant's usual daily activity and may require systemic drug therapy or other treatment. Severe events are usually potentially life-threatening or incapacitating. Of note, the term "severe" does not necessarily equate to "serious".]

8.3.4.2 Relationship to Study Intervention

[All adverse events (AEs) must have their relationship to the TMS administration assessed by the PI. The degree of certainty about causality will be graded using the categories below.

- Definitely Related There is clear evidence to suggest a causal relationship, and other possible contributing factors can be ruled out.
- Probably Related There is evidence to suggest a causal relationship, and the influence of other factors is unlikely.
- Possibly Related There is some evidence to suggest a causal relationship (e.g., the event occurred within a reasonable time after administration of the trial medication). However, other factors may have contributed to the event (e.g., the participant's clinical condition, other concomitant events). Although an AE may rate only as "possibly related" soon after discovery, it can be flagged as requiring more information and later be upgraded to "probably related" or "definitely related", as appropriate.
- Unlikely to be related A clinical event whose temporal relationship TMS administration makes a causal relationship improbable (e.g., the event did not occur within a reasonable time after administration of the intervention) and in which other drugs or chemicals or underlying disease provides plausible explanations (e.g., the participant's clinical condition, other concomitant treatments).

[MagPro X100 Stimulator, Cool-B65 Butterfly Coil]

Page 27 of 39

• Unrelated – The AE is completely independent of TMS administration, and/or evidence exists that the event is definitely related to another etiology. There must be an alternative, definitive etiology documented by the clinician.]

8.3.4.3 Expectedness

[The PI will be responsible for determining whether an adverse event (AE) is expected or unexpected. An AE will be considered unexpected if the nature, severity, or frequency of the event is not consistent with the risk information previously described for TMS.]

8.3.5 Time Period and Frequency for Event Assessment and Follow-Up

[Safety will be assessed by monitoring and recording potential adverse effects at each study visit. Information on all adverse events will be recorded in the source documentation. To the extent possible, each adverse event or follow-up information will be evaluated by the PI. This allows site to determine relationship to treatment, expectedness, and seriousness of the event. It also allows the site to evaluate patient safety and work with the patient to a resolution.]

8.3.6 Adverse Event Reporting

[Adverse events will be reported from the time of informed consent until study completion. The investigator will report AEs to the IRB and other local regulatory groups per the local requirements.]

8.3.7 Serious Adverse Event Reporting

[The PI will report unexpected and related adverse events to the necessary regulatory groups.]

8.3.8 Reporting Events to Participants

[Adverse events (both individual and aggregate level) will be shared with participants as the PI finds necessary.]

8.3.9 Events of Special Interest

[As per MRI procedure dictates, it is possible that during the course of the research study, the research staff may notice unexpected finding(s) on a participant's images. Should this occur, the finding(s) will be considered by the appropriate personnel and the PI will inform participants if necessary for medical follow-up. These possible finding(s) will not be disclosed to the participant unless deemed necessary by the PI and reviewing radiologist in order to avoid unnecessary anxiety for participants.

Other notable events, such as device malfunctions, will be documented and reported as needed.]

[MagPro X100 Stimulator, Cool-B65 Butterfly Coil]

Page 28 of 39

8.3.10 Reporting of Pregnancy

[N/A - All women of child bearing potential are asked if they are using a reliable method of birth control and are asked to attest that they are not pregnant before study visit and on the TMS safety screening form. Due to potential safety reasons, pregnant women will not be included in the study.]

8.4 Unanticipated Problems

8.4.1 Definition of Unanticipated Problems (UP)

[The Office for Human Research Protections (OHRP) considers unanticipated problems involving risks to participants or others to include, in general, any incident, experience, or outcome that meets all the following criteria:

- Unexpected in terms of nature, severity, or frequency given (a) the research procedures that are described in the protocol-related documents, such as the Institutional Review Board (IRB)-approved research protocol and informed consent document; and (b) the characteristics of the participant population being studied;
- Related or possibly related to participation in the research ("possibly related" means there is a reasonable possibility that the incident, experience, or outcome may have been caused by the procedures involved in the research); and
- Suggests that the research places participants or others at a greater risk of harm (including physical, psychological, economic, or social harm) than was previously known or recognized.]

8.4.2 Unanticipated Problem Reporting

[Unanticipated problems (UPs) should be reported by the PI to the necessary regulatory groups, within the timeline required by local regulations.]

8.4.3 Reporting Unanticipated Problems To Participants

[Unanticipated problems (both individual and aggregate level) will be shared with participants as the PI finds necessary.]

8.5 Device Reporting

[Safety reporting for the device(s) will be according to 21 CFR 812.150.]

9 STATISTICAL CONSIDERATIONS

9.1 Statistical Hypotheses

Primary Efficacy Endpoint(s):

[MagPro X100 Stimulator, Cool-B65 Butterfly Coil]

Page 29 of 39

[The primary outcome will be based on the set of repeated Montgomery Asberg Depression scores obtained at baseline and on each of the five treatment days.

Hypothesis 1: The null hypothesis is that there will be no difference in reductions in depressive symptoms by the end of the five-day treatment period. The alternative hypothesis is that, compared with sham, active TMS will result in a greater reduction in depressive symptoms by the end of the treatment period. This is a superiority comparison, for active relative to sham.]

• Secondary Efficacy Endpoint(s):

[The main secondary outcome will be the change in correlation of the dorsal lateral prefrontal cortex (DLPFC) with limbic regions, in particular with the subgenual cingulate cortex (SGACC).

Hypothesis 2: The null hypothesis is that there will be no difference in the change in correlation from pre-treatment to post-treatment between the active and sham groups. The alternative hypothesis is that, compared with sham, active TMS will result in a greater increase in correlation of the dorsal lateral prefrontal cortex (DLPFC) with limbic regions, in particular with the subgenual cingulate cortex (SGACC). This is a superiority comparison, for active relative to sham.]

9.2 Sample Size Determination

[The sample size provides power for a large effect on the primary hypothesis, comparing the treatment groups on improvements in their MADRS scores across five days of treatment. Analyses will be based on linear mixed effects models, as described below.

Power for Hypothesis 1: We use the methods of Hedeker, Gibbons and Waternaux [13]. For a random intercept model with correlation coefficient of rho=0.3, we have 80% power for a group effect of Cohen's d=0.72.

Further analyses are regarded as exploratory. The sample will provide preliminary effect size estimates for secondary endpoints, for future studies.]

9.3 Populations for Analyses

[The analyses will follow the Intention-to-Treat principle, with all randomized participants contributing to analyses. In particular, the linear mixed effects models to be used for the primary hypothesis will make use of all data, partial or complete, provided by the participants.]

9.4 Statistical Analyses

9.4.1 General Approach

[The analyses of the outcomes of Aims 1 and 2 will use linear mixed effects models for repeated measures. Outcomes will be measured at baseline and for each of the 5 days of TMS treatment. The model will incorporate baseline covariates (age, gender, ATHF score, use of psychotropic medication, handedness, head motion), along with randomized treatment assignment. The data collected to be

[MagPro X100 Stimulator, Cool-B65 Butterfly Coil]

Page 30 of 39

included in efficacy analyses (pre- and post-treatment) will be the measures of depression severity (MADRS), Antidepressant Treatment History Form (ATHF) data, psychotropic medication at baseline and resting state functional connectivity data (using DLPFC as a seed regions). If other variables are found to be related to the outcome and are imbalanced with respect to treatment assignment, we will perform additional analyses with these variables added to the model. For the continuous outcomes, data transformations will be implemented if there are substantial deviations from normality.

Effect size estimates and associated confidence intervals will be reported for all primary and secondary outcomes.

The trajectory of changes over the 5 days of treatment will be assessed with descriptive statistics and graphical displays. We will plot the mean daily changes in each score by treatment group to provide insight into the typical trajectory of treatment response. Because this is a short-term study we do not anticipate much (if any) missing data.]

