5 STUDY POPULATION

5.1 Inclusion Criteria

[In order to be eligible to participate in this study, an individual must meet all of the following criteria:

- Bipolar depression (BP I and BP II) by DSM 5 criteria [8]
- Age 18-70
- Right or left handed
- All genders
- Treatment resistant depression, as in they must have treatment resistant depression with 2 or more prior antidepressant trials that have failed to produce a response (> 50% reduction in symptoms) using ATHF criteria [9]
- Able to provide informed consent to participate in the study
- Must be on a stable medication regimen, requiring at least one mood stabilizer
- Depression severity as represented by scoring at least 20 on MADRS

If unsure about participants' eligibility, the research team may contact the participants' treatment provider (i.e. psychologist, nurse practitioner, psychiatrist) to gather additional information to make a determination.]

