9.4.2 Analysis of the Primary Efficacy Endpoint(s)

[Aim 1: To assess clinical efficacy of HDS-TBS.

Hypothesis 1: Compared with sham, active TMS will result in a greater reduction in depressive symptoms by the end of the treatment period. Each patient will receive either one five day sham or one 5-day active treatment.

The primary outcome will be based on the set of repeated Montgomery Asberg Depression scores obtained at baseline and on each of the five treatment days. We will use linear mixed effects models to compare the two treatment groups on change from baseline across the five days. As noted above, the response may be transformed to reduce levels of skewness. The main fixed effects will be the treatment group indicator, and we expect that a random intercept will accommodate the within person correlations over the five daily measures of change.

Power for Hypothesis 1: We use the methods of Hedeker, Gibbons and Waternaux [13]. For a random intercept model with correlation coefficient of rho=0.3, we have 80% power for a group effect of Cohen's d=0.72.

Estimated regression coefficients will be reported, along with standard errors, associated confidence intervals, and p-values for hypothesis tests. In analyses adjusting for covariates, adjusted least squares means for treatment groups will be reported.

Little missing data is expected for the baseline and five-day treatment period. The mixed effects models used for Hypothesis 1 will use any data, partial or complete, provided by the randomized participants, and will yield valid estimates under missing-at-random assumptions.]

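### The primary model analyses MADRS change from baseline but leaves baseline MADRS out of the covariates, although every patient has the score

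*Combined protocol and SAP*

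**What the plan says.** Section 9.4.2 will use linear mixed models to "compare the two treatment groups on change from baseline across the five days". It names the treatment indicator as the main fixed effect and expects that "a random intercept will accommodate the within person correlations over the five daily measures of change". No time or treatment-by-time term is named.

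Section 9.4.1 gives the covariates: "The model will incorporate baseline covariates (age, gender, ATHF score, use of psychotropic medication, handedness, head motion), along with randomized treatment assignment". Section 9.4.2 adds: "In analyses adjusting for covariates, adjusted least squares means for treatment groups will be reported". The primary test could therefore be run with or without the six, and neither version contains baseline MADRS. The only route for further variables is the clause in Section 9.4.1 that begins "If other variables are found to be related to the outcome and are imbalanced with respect to treatment assignment", and it leads to additional analyses.

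The score exists for everyone, because Section 5.1 requires "Depression severity as represented by scoring at least 20 on MADRS". Section 8.1 places the MADRS in the list introduced by "Participants complete the following for screening". In the Schedule of Activities (Section 12.1) the MADRS is marked at Screening and on Day 1, but not in the Enrollment/Baseline column. Sections 9.1 and 9.4.2 count baseline apart from the five treatment days. Screening is thus the baseline rating by elimination, but no section says so.

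**The concern.** Analysing change without the baseline value as a covariate assumes that a patient who starts one point higher also ends one point higher. If the true slope is below 1, change stays correlated with baseline, and that explainable variance remains in the error term. The model finds room for handedness and head motion but not for the baseline value of its own outcome.

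The validity of the test is not in question, since the contrast is unbiased under randomization. Nor is sensitivity to chance baseline imbalance a second harm, because it is the same variance seen from another side. What is at stake is precision in the only powered comparison of a trial with 32 usable patients (Section 1.1).

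**Working it through.** **Inputs from the documents.** 32 usable patients (Section 1.1); five daily measures and a random intercept (Section 9.4.2); d = 0.72 and rho = 0.3 (Section 9.2: "For a random intercept model with correlation coefficient of rho=0.3").

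**Assumptions.** 16 per arm and two-sided 0.05. On the main reading, rho and d refer to the change scores, because Section 9.4.2 attaches the random intercept to the change measures. Each listed covariate takes one degree of freedom.

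**The plan's own figure.** With complete data the treatment effect is a difference in five-day mean change. With change SD 1, its variance factor is V = (1 + 4 × 0.3)/5 = 0.44. The noncentrality is 0.72/√((2/16) × 0.44) = 3.07 on 30 df, so power is 84.4%. The plan states 80%. Its figure is conservative on this reading, and it cannot be called wrong because alpha and sidedness are not given.

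**Adding baseline MADRS.** If baseline explains a share R² of the between-patient variance in mean change, V becomes 0.44(1 − R²). Fitting q covariates multiplies the variance by 29/(29 − q) on average and leaves 30 − q df.

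| | Without baseline MADRS | R² = 0 | 10% | 20% | 30% | Break-even R² |
|---|---|---|---|---|---|---|
| No other covariates (q = 0 to 1) | 84.4% | 83.0% | 86.7% | 90.3% | 93.6% | 3.7% |
| Six covariates that explain nothing (q = 6 to 7) | 74.6% | 72.6% | 77.0% | 81.7% | 86.4% | 4.7% |

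The extremes are 72.6 − 74.6 = −2.0 and 86.4 − 74.6 = +11.8 points.

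**Which R² values fit rho = 0.3?** Let post-baseline SD be 1, baseline SD be k, and all raw correlations be r.

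- Variance of mean change: (1 + 4r)/5 + k² − 2rk.
- Variance after adjustment: (1 + 4r)/5 − r².
- Correlation between daily changes: (r + k² − 2rk)/(1 + k² − 2rk).

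Setting the last expression to 0.30 gives r = (0.3 − 0.7k²)/(1 − 1.4k). Along that curve, with d kept in change-score SDs:

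| k | r | R² | Power, no other covariates | Power, six covariates |
|---|---|---|---|---|
| 0.40 | 0.43 | 0.2% | 84.4 to 83.1% | 74.6 to 72.7% |
| 0.50 | 0.42 | 1.9% | 84.4 to 83.7% | 74.6 to 73.4% |
| 0.55 | 0.38 | 7.1% | 84.4 to 85.7% | 74.6 to 75.7% |
| 0.60 | 0.30 | 20.5% | 84.4 to 90.5% | 74.6 to 81.9% |

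At k = 0.60 the variances are 0.44 and 0.35. With six covariates the relative efficiency is (0.44 × 29/23)/(0.35 × 29/22) = 1.20, similar to adding about 6 patients to 32. A simulation of 40,000 trials per setting agrees: 84.5 to 90.6%, and 74.6 to 81.8%.

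**Outer bound.** If rho = 0.3 instead describes raw scores with equal SDs (k = 1), the variances are 0.84 and 0.35, and d is in raw-score SDs. Power then goes from 57.6 to 90.5%, or from 47.6 to 81.9% with six covariates. This implies a correlation of 0.50 between changes, so it does not fit the main reading.

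**The case against.** **The gain may be nil.** The documents give neither k nor r. For k from about 0.3 to 0.52 on the curve above, R² is below break-even and the covariate costs 0 to 2 points. The entry floor of 20 truncates baseline and narrows its SD, which argues against values of k near 1. This stands. The k = 0.60 case is an illustration, and the outer bound should not be quoted as an expected gain. It does not overturn the point, because the possible loss is about 2 points and the possible gain on the main reading about 12.

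**Baseline may already be a response.** Sections 9.1 and 9.4.2 include the baseline score in the outcome set, and Section 9.4.1 speaks of outcomes measured at baseline and on each day. In a model with baseline as a response, treatment-by-time terms and a common baseline mean, no covariate would be needed. But Section 9.4.2 names five measures of change and a treatment indicator, with none of those terms. Change scores are the more natural reading. If the other model is meant, the plan should specify it.

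**The clause on imbalanced variables may cover it.** It could bring baseline MADRS into an additional analysis. The primary test would stay as it is, and a choice made after seeing the data does not replace prespecification.

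**Conclusion.** The concern holds. The primary model as written never estimates the slope on baseline MADRS, although the score is on file for every eligible patient. This is a moderate point about efficiency: bias and type I error are unaffected. On the main reading the change in power lies between about −2 and +12 points for R² from 0 to 30%, with break-even near 4 to 5%. The range rests on 1:1 allocation, two-sided 0.05, rho and d on the change scale, and unreported SDs and correlations. The missing definition of baseline is a smaller matter of clarity that the same edit can settle.

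**What to change.** In Section 9.4.2, before unblinding, prespecify baseline MADRS as a fixed covariate in the primary mixed model, whether or not the six listed covariates are also fitted. Alternatively, specify a constrained longitudinal model with baseline as a response and a common baseline mean. That version needs a covariance structure that lets the baseline variance differ from the later ones, which a random intercept alone does not. In the same sentence, confirm that baseline is the Screening MADRS.

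The cost is one SAP sentence and, for the covariate version, one degree of freedom. No new data are needed, and no visit or eligibility rule changes.

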1 STUDY SUMMARY

1.1 Synopsis

Title: [Intensive TMS for Rapid Relief of Bipolar Depression Symptoms]

Short Title: [Intensive TMS for Bipolar Depression]

Study Description:

[The research study is being conducted to test whether using high dose spaced theta-burst rTMS (a form of transcranial magnetic stimulation) produces a significant reduction in depressive symptoms compared with sham. This project will recruit patients aged 18-70 with symptoms of bipolar depression who have failed (or not shown signs of improvement) after at least two prior treatments. The null hypothesis is that there will be no difference in reductions in depressive symptoms by the end of a five-day treatment period. The alternative hypothesis is that, compared with sham, active TMS will result in a greater reduction in depressive symptoms by the end of the treatment period.]

Objectives:

[The overall objective of this project is to test whether using high dose spaced theta-burst rTMS (HDS-TBS) produces a significant reduction in depressive symptoms compared with sham.]

Primary Endpoint:

[Aim 1: To assess clinical efficacy of HDS-TBS.]

Secondary Endpoints:

Population:

[Aim 2: To determine the effect of iTBS on DLPFC rsfMRI and establish

a relationship between change in brain resting state functional

connectivity and treatment effects.]

Study

[34 subjects (with 32 usable data), within the ages of 18-70, right or left handed, gender inclusive, diagnosed with Bipolar I & II depressed (per

DSM 5 criteria)]

Phase: [N/A]

Description of

[Center of Neuromodulation in Depression & Stress, University of

Sites/Facilities Pennsylvania]

[MagPro X100 Stimulator, Cool-B65 Butterfly Coil]

Page 9 of 39

Enrolling Sites: [Center of Neuromodulation in Depression & Stress, University of

Pennsylvania]

Description of

Study Intervention:

[Intensive iTBS. This includes intermittent theta-burst stimulation (iTBS), a patterned form of repetitive transcranial magnetic stimulation (rTMS)

over the left dorsal lateral prefrontal cortex (L-DLPFC).]

Study Duration: [1 year]

Participant Duration:

[figure not shown]
[6-8 weeks]

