6.3 Measures to Minimize Bias: Randomization and Blinding

[Patients who are enrolled in the study (i.e., met inclusion/exclusion criteria) will be randomized to active TMS or Sham by a randomization system determined by the Independent Randomization Provider (IRP). This will occur at least one day before the start of treatment.

Only trained staff will administer the TMS treatment and the required clinical assessments during the study visits. These staff (as well as the PI and the patients) will also be blinded until the end of the study. Included in blinded status is the TMS operator since "active" vs "sham" delivery will be randomized and delivered in a blinded fashion. The only exception will be [name] (the study statistician) and [name] (clinical and medical monitor).]

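### Sections 9.4.1 to 9.4.3 disagree on covariates; as written, the MADRS model carries head motion and handedness, which cost about 3 to 4 points of power if they do not predict MADRS change

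*Combined protocol and SAP*

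**What the plan says.** Section 9.4.1 opens with a rule for both aims: "The analyses of the outcomes of Aims 1 and 2 will use linear mixed effects models for repeated measures". It then gives a single list: "The model will incorporate baseline covariates (age, gender, ATHF score, use of psychotropic medication, handedness, head motion), along with randomized treatment assignment". Aim 1 is the MADRS comparison and Aim 2 is resting-state connectivity.

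Section 9.4.2, on the primary analysis, names the treatment group indicator as the main fixed effect and adds that "we expect that a random intercept will accommodate the within person correlations over the five daily measures of change". It mentions covariate-adjusted analyses when it describes how least squares means will be reported. It does not say whether the primary test is one of them.

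Section 9.4.3 gives the connectivity regression four covariates: age, gender, ATHF score and psychotropic medication. Handedness and head motion are not among them.

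Sections 4.1, 8.1 and 8.2 each say that handedness will enter the data analysis, without saying which model.

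Section 9.2 describes the power model as follows: "For a random intercept model with correlation coefficient of rho=0.3", "we have 80% power for a group effect of Cohen's d=0.72". It mentions no covariates and no share of variance explained by covariates. The synopsis gives the sample as "34 subjects (with 32 usable data), within the ages of 18-70". Section 9.3 has all randomized participants contributing to the analyses.

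**The concern.** Three neighbouring sections describe the covariates differently, so the model for the primary test is not fixed. On a literal reading the head-motion term sits in the wrong place: it is in the model for a clinician-rated depression score and missing from the regression on scan data.

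Two things are at stake. The first is precision. With 32 usable patients, a covariate that does not predict the outcome still costs something, because chance imbalance between the arms inflates the variance of the treatment effect and each term uses a degree of freedom. The second is who is analysed. A regression drops a patient whose covariate is missing unless a rule says otherwise, and the plan has no such rule. A patient with MADRS scores but no usable scan would leave the primary model, contrary to 9.3.

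The power statement does not help the reader judge this, because it describes a model without covariates.

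**Working it through.** **Inputs from the plan.** 32 usable patients of 34 (synopsis); d = 0.72, rho = 0.3, random intercept, 80% power (9.2); five daily measures of change (9.4.2); six named covariates (9.4.1).

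**Assumptions.** Two-sided 5%, because 9.1 says only "This is a superiority comparison, for active relative to sham". 1:1 allocation, because 6.3 gives no ratio. One term per covariate and no missing data. R2 is the share of variance in a patient's five-day mean change that the covariates explain. The plan gives no value, so a range is used.

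**Step 1: the plan's own figure.** The variance factor for the mean of m = 5 equicorrelated measures is

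(1 + (m − 1) × rho)/m = (1 + 4 × 0.3)/5 = 0.44.

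With 16 per arm, the standard error of the group difference in SD units is √(0.44 × 2/16) = √0.055 = 0.2345, so the noncentrality is 0.72/0.2345 = 3.07. Power is 86.7% by the normal approximation and 84.4% by the noncentral t with 30 df. The stated 80% is not reproduced exactly. It is conservative under these inputs: the difference detectable with 80% power is d = 0.68 (t-based).

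**Step 2: cost of covariates.** With k non-prognostic covariates in N patients, the expected variance inflation is (N − 3)/(N − 3 − k), and the degrees of freedom are N − 2 − k.

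- Six covariates: 29/23 = 1.26.
- Four covariates (head motion and handedness dropped): 29/25 = 1.16.
- Ratio, the share due to those two terms: (29/23)/(29/25) = 25/23 = 1.087, or about 9%. That is like losing 32 × (1 − 23/25), about 2.6, of 32 patients.

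**Step 3: power at d = 0.72, 16 per arm.** The residual variance is multiplied by (1 − R2). The four-covariate row uses the same R2 as the six-covariate row, which means that the two dropped terms explain nothing.

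| Model | R2 = 0 | R2 = 0.10 | R2 = 0.20 |
|---|---|---|---|
| Six covariates | 74.6% | 79.0% | 83.5% |
| Four covariates | 78.3% | 82.4% | 86.6% |
| Gain from dropping two | 3.7 | 3.4 | 3.1 |

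The reference without covariates is 84.4%. Simulation of the patient means agrees at R2 = 0: 84.5% with no covariates and 75.4% with six.

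**Step 4: when does the six-covariate model fall below 80%?**

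- 16 per arm: when R2 is below about 0.12.
- 17 per arm (all 34 analysed): 78.1% at R2 = 0, so when R2 is below about 0.05.
- 16 per arm, if the power without covariates is taken to be exactly 80% instead of the recomputed 84.4%: when R2 is below about 0.22.

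At 16 per arm, R2 of about 0.22 brings six-covariate power back to the 84.4% of the model without covariates. Above that, adjustment gains power.

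**The case against.** The strongest reply is that 9.4.2 is the specific section for the primary analysis and names only the treatment indicator. If the primary test is unadjusted, the power statement fits it and there is no loss. This stands as a reading, so it cannot be said that the MADRS model must carry these terms. But 9.4.1 is worded as a rule covering Aim 1, and 9.4.2 does not revoke it. The plan supports both readings.

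A second reply is that adjustment may raise power, since age or ATHF score could be prognostic. That is correct, and it defeats any claim that the full list must harm the trial. It does not defend the two terms: the gain from dropping them is 3 to 4 points at every R2 tabulated, provided that they explain nothing themselves.

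Third, handedness looks deliberate, since three sections say it will be analysed. This also stands. Those sections do not place it in the MADRS model, but any edit must be reconciled with them.

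Fourth, baseline imaging is needed for coil targeting, so few treated patients may lack a head-motion value. That limits the number who would be lost. It does not supply a rule for a patient randomized without a usable scan.

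Finally, the count of six is uncertain. Section 5.1 requires a mood stabilizer for everyone, so a yes/no psychotropic term would be constant. Five terms give 76.6% at R2 = 0.

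**Conclusion.** The inconsistency among 9.4.1, 9.4.2 and 9.4.3 is established, and so is the literal presence of head motion and handedness in the MADRS model. That head motion is a scan-quality variable with no bearing on MADRS is an inference; the plan gives no link either way. If neither term predicts MADRS change, together they cost about 9% in variance and 3 to 4 points of power, under the assumed two-sided 5% and 1:1 allocation.

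A reader might infer three stronger things that the documents do not support:

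- **That the trial's power is below the stated 80%.** This depends on an R2 that the plan does not give. The threshold is about 0.12 with 32 patients and about 0.05 with 34 (about 0.22 with 32 if power without covariates is exactly 80%).
- **That leaving covariates out of the power statement lowers power.** It only leaves their effect unassessed.
- **That an imaging covariate list was carried over to MADRS.** The connectivity regression in 9.4.3 lists neither head motion nor handedness.

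This should be corrected before analysis. It does not show that the trial is underpowered.

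**What to change.** 1. In 9.4.1 and 9.4.2, give the MADRS model its own covariate list, and say that this is the model for the primary test. Leave head motion out. Leave handedness out too unless it is expected to predict MADRS change, and if it stays, say why.
2. Reconcile the handedness statements in 4.1, 8.1 and 8.2 with that choice, for example by saying that handedness is reported descriptively for MADRS.
3. Put head motion in the connectivity model in 9.4.3, which now omits it, and align 9.4.1 with that section.
4. State in 9.2 that the 80% figure is for a model without covariates.

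The cost is wording only. The small downside is that handedness would be described, not adjusted for, in the MADRS analysis.
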